4.3 End of treatment

The number and percentage of patients who completed or not the treatment will be provided. In those who finished treatment early, the causes of termination will be described.

All the analyses will be performed separately for each arm and a total column may be added if needed.

4.4 End of study

The number and percentage of patients who completed or not the study will be provided. For those patients who finished study early, the causes of termination will be described.

All analysis will be performed separately for each arm and a total column may be added if needed.

4.5 Deaths

The number and percentage of patients who died during the study and the reasons will be provided. Patients who have died due to an adverse event will be described in more detail, indicating all the variables related to the AEs registered in the application.

All the analyses will be performed separately for each arm and a total column may be added if needed.

4.6 Missing data

Missing data imputation is not foreseen.

5 PATIENTS DESCRIPTION

5.1 Demographic data description. General considerations.

The characteristics of the patients in the safety population will be described and the not available information will be detailed. Continuous variables will be presented through the mean, median, standard deviation, range, Q1, Q3 and categorical variables will be presented through the distribution of frequencies and percentages; not available values will not be taken into account in the percentage calculation, only valid percentages will be presented. The analysis will be carried out on the full safety population and all results will be provided by treatment arm. Aggregated results as well as patient listings will be provided.

5.2 Patients characteristics

In this section the following variables will be described:

a) Demographic data:

- Age (years) (continuous).
- Age (<65 years; ≥ 65 years).
- Gender (Male/Female).
- Ethnic group (Arabic; White; Latin; Asian; Black; Other).

b) Clinical data: Patient status:

- FDA classification: Mild, Moderate and Severe.
- Six-point ordinal scale: On day 1 (first administration day), patients will be classified according to the following six-point ordinal scale:

1. Discharge (Alive)
2. Hospital admission, not requiring supplemental oxygen.
3. Hospital admission, requiring supplemental oxygen.
4. Hospital admission, requiring high-flow nasal cannula or non-invasive mechanical ventilation.
5. Hospital admission, requiring extracorporeal membrane oxygenation or invasive mechanical ventilation.
6. Death.

c) Clinical data: Signs and symptoms on admission:

- Time from the beginning of the first symptom: The time from the beginning of the first symptom is defined as the difference, in days, between the date of the first dose of plitidepsin administration and the date of the beginning of the first symptom.
- Time from the beginning of the first symptom to hospital admission (days).
- Fever history (Yes/No).
- Dehydration (Yes/No).
- Cough (Yes/No). In affirmative case, describe:
- Sputum production (Yes/No). In affirmative case, describe:
- Bloody sputum/ Hemoptysis (Yes/No).
- Runny nose (rhinorrhea) (Yes/No).
- Earache (Yes/No).
- Crackles (Yes/No).
- Thoracic pain (Yes/No).
- Muscular pain (myalgia) (Yes/No).
- Joint pain (arthralgia) (Yes/No).
- Fatigue / malaise (Yes/No).
- Short of breath (dyspnea) (Yes/No).
- Intercostal retraction (Yes/No).
- Headache (Yes/No).
- Altered state of consciousness / confusion (Yes/No).
- Convulsion (Yes/No).
- Abdominal pain (Yes/No).
- Vomiting / nausea (Yes/No).
- Diarrhea (Yes/No).
- Conjunctivitis (Yes/No).
- Rash (Yes/No).
- Skin ulcer (Yes/No).
- Lymphadenopathy (Yes/No).
- Throat pain (Yes/No).
- Bleeding (hemorrhage) (Yes/No). If so, the description of the bleeding locations will be detailed.

d) Clinical data: Comorbidities:

- Chronic cardiac pathologies including congenital cardiac pathologies (does not include hypertension) (Yes/No).
- Arterial hypertension (Yes/No).
- Chronic lung disease (does not include asthma) (Yes/No).
- Asthma (medical diagnosis) (Yes/No).

- Diabetes with complications (Yes/No).
- Diabetes without complications (Yes/No).
- Chronic kidney disease (Yes/No).
- Rheumatic disorder (Yes/No).
- Moderate or severe liver disease (Yes / No).
- Mild liver disease (Yes/No).
- Dementia (Yes/No).
- Malnutrition (Yes/No).
- Chronic neurological disorder (Yes / No).
- Smoker (Yes/No).
- Malignant neoplasm (Yes/No).
- Chronic hematological disease (Yes / No).
- AIDS / HIV (Yes / No).
- Obesity (define by medical staff) (Yes/No).
- Other risk factors (Yes / No). If so, the description of the specified factors will be detailed.

e) Vital signs at baseline

- SBP (mmHg) (continuous).
- DBP (mmHg) (continuous).
- Heart rate (l.p.m.) (continuous).
- Respiratory rate (r.p.m.) (continuous).
- Temperature (°C) (continuous).
- Saturation O₂ (%) (continuous).
- Saturation (Room air/Oxygen therapy/Not available). In the case of oxygen therapy, the following will be described:
 - Oxygen therapy type (Nasal glasses; Simple mask; Venturi mask; Reservoir mask; Other). In case of other a detailed listing will be provided.
 - Flow (L/min) (continuous).
 - FiO₂ (%) (continuous).
 - PaO₂ (mmHg) (continuous)
 - PaO₂/FiO₂ o SaO₂/FiO₂ (continuous).
- Chest X-ray (Yes/No). if so, the following will be described:
 - X-ray result (Normal/Abnormal). In case of abnormality, the abnormality will be detailed (Unilateral Pneumonia / Bilateral Pneumonia / Other). In case of other abnormality, the description of the abnormalities will be provided.
- Electrocardiogram (Yes / No). If so, it will be described:
 - Result (Normal / Abnormal: Not clinically significant or Abnormal: clinically significant). In case of abnormality, the description of the abnormalities will be provided. (QT interval prolongation / PR interval prolongation / other alteration). In case of other alteration, the description of the other alteration will be provided.

f) Viral load (log copies / mL)

g) Summary of Demographic and Other Baseline Characteristics

- Age, median (range) years

- Gender, % male
- Median (range) time from symptom onset to first plitidepsin administration, days
- Number of comorbidities, n (%) (none, one, two or more)
- Comorbidities, n (%) (Cardiac disease, Kidney disease, Liver disease, Lung disease (COPD), Asthma, Diabetes, Hypertension, Obesity)
- Clinical status at randomization, n (%)
- Vital signs, median (range) (Body temperature, °C, Systolic blood pressure, mmHg, Diastolic blood pressure, mmHg, Heart rate, bpm, Respiratory rate, bpm, SpO2 B, %, On oxygen at baseline, n (%))
- Laboratory parameters, median (range) (WBC, x109/L, Platelet count, x109/L, Lymphocytes, x109/L, Serum creatinine, µmol/L, ALT x ULN, AST x ULN, LDH x ULN, CPK x ULN, GGT x ULN, C-reactive protein, Ferritin, D-dimer)
- log10 copies/mL viral load, median (range)

6 TREATMENT DESCRIPTION

6.1 Administered treatment

The analysis of treatment administration will be carried out on the safety population and by treatment arm. The following variables will be analyzed:

- Days of treatment with plitidepsin (categorical).
- Total administered dose (continuous).
- Relative dose intensity (continuous). It will be calculated as the proportion between the total dose administered and the theoretical dose expected per protocol.

The variables will be analyzed on each of the treatment days (days 1 to 3): Administered treatment (Yes / No). If not, the reasons for non-administration will be described. If so, the variables will be described:

- Administered treatment dose (mg/day) (continuous).
- Treatment administration interrupted (Yes/No). If so, the reasons for interruption will be described.
- Pre-medication (Yes/No). If so, the description of the coded active substances (ATC) and grouped by type (antiemetic, gastric protector, antihistamine and corticosteroids) will be provided.

7 SAFETY EVALUATION

The safety analysis will be performed on the safety population defined in section 4.1. They will be presented by treatment arm as well as by treatment arm based on age groups (<65 years; ≥ 65 years) and the total population.

7.1 Safety evaluation. General considerations

Adverse events will be coded by using MedDRA (latest version available) and will be presented grouped by system (SOC) and preferred term (PT). The associated grades with each of the adverse events will be evaluated using the NCI-CTCAE V5.0 toxicity criteria.

To obtain the adverse events per patient, the maximum grade will be considered for each of the events collected for each patient. If the relationship between an adverse event and the study drug cannot be ruled out, it will be considered to be related for the analysis.

The analysis will be presented on days 3, 7, 15 and 31 after the start of study treatment:

The following results will be provided:

- Number and percentage of patients presenting the following adverse events with ≥ 1 grade change in:
 - Hematological parameters:
 - Neutropenia
 - Thrombocytopenia
 - Anemia
 - Lymphopenia
 - Non-hematological parameters:
 - CPK increase
 - AST increase
 - ALT increase
 - Total increase, or direct bilirubin
 - Neurotoxicity
 - QT-QTc interval prolongation
- Number and percentage of patients unable to complete treatment
- The number and percentage of patients with some AE or SAE will be presented:
 - From Day 1 to day 3
 - From Day 1 to day 7
 - From Day 1 to day 15
 - From Day 1 to day 31
- The number and percentage of patients with some SAE will be presented:
 - From Day 1 to day 3
 - From Day 1 to day 7
 - From Day 1 to day 15
 - From Day 1 to day 31
- The number and percentage of patients with some Grade ≥ 3 Adverse Events, Regardless of Relationship will be presented.
 - From Day 1 to day 3

- From Day 1 to day 7
 - From Day 1 to day 15
 - From Day 1 to day 31
- Patients with ≥ 1 grade change from baseline in hematologic parameters, from Day 1 to.
 - From Day 1 to day 3
 - From Day 1 to day 7
 - From Day 1 to day 15
 - From Day 1 to day 31
 - Patients with ≥ 1 grade change from baseline in non-hematologic parameters, from Day 1 to
 - From Day 1 to day 3
 - From Day 1 to day 7
 - From Day 1 to day 15
 - From Day 1 to day 31
 - The number and percentage of patients with some Treatment-Related Adverse Events will be presented.
 - The number and percentage of Treatment-Related Adverse Events will be presented.
 - The number and percentage of Adverse Events, Regardless of Relationship, by grade will be presented.
 - The number and percentage of patients with some grade ≥ 3 Adverse Events, Regardless of Relationship will be presented.
 - The number and percentage of grade ≥ 3 Adverse Events, Regardless of Relationship will be presented.
 - The number and percentage of patients with some Treatment-Related Adverse Events, by grade, (treatment dose and Pre/Post relevant amendment n°9 (13AUG2020) and relevant amendment n°12 (11SEP2020)) will be presented.
 - The number and percentage of patients with some Adverse Events, Regardless of Relationship, by grade, (treatment dose and Pre/Post relevant amendment n°9 (13AUG2020) and relevant amendment n°12 (11SEP2020)) will be presented.
 - A detailed listing of patients with all adverse events related or not with plitidepsin indicating serious (yes / no), relation and grade will be provided.
 - A detailed listing of patients with all the related adverse events with plitidepsin indicating serious (yes / no), relation and grade will be provided.
 - A detailed listing of patient with all the non-related adverse events with plitidepsin indicating serious (yes / no), relation and grade will be provided.
 - A detailed listing of patients who have died from a SAE will be provided.
 - A detailed listing of patients who have suffered an adverse event that have caused treatment withdrawn or interruption will be provided.

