## **6.2.Primary endpoint**

### Primary endpoint:

To determine the safety and toxicological profile of plitidepsin at each dose level administered in patients admitted for COVID-19, the following endpoints will be analysed:

- Frequency of the following  $\geq$  grade 3 adverse events according to the NCI-CTCAE criteria v 5.0 at 3, 7, 15 and 31 days:
  - Haematological
    - Neutropenia
    - Thrombopenia
    - Anaemia
    - Lymphopenia
  - Non-haematological
    - CPK increase
    - ALT and/or AST increase
    - Total bilirubin or direct bilirubin increase
    - Neurotoxicity

- QT-QTc interval prolongation
- Other  $\geq$  grade 3 adverse events
- Percentage of patients in which treatment cannot be completed and reasons.
- Percentage of patients with AEs and SAEs at days 3, 7, 15 and 31.
- Changes from baseline (day -1 or day 1 before administration of the study drug) in haematological and non-haematological parameters on days 3, 7, 15 and 31.
- Percentage of patients with ECG abnormalities on days 2, 3, 4, 5, 6, 7, 15 and 31.

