### **12.4. Analysis of the primary endpoint**

The safety analysis will be performed in the safety population, that is, in patients who have received at least one dose of treatment. Patients will be analysed in the administered treatment arm.

Safety and tolerability analyses will be presented by treatment arm as well as by treatment arm according to age group (<65 years; ≥65 years). Adverse events will be coded using the latest version of the MedDRA dictionary and assessed using the NCI-CTCAE criteria v. 5.0.

The number and percentage of patients presenting the following ≥ grade 3 adverse events will be provided, according to the NCI-CTCAE criteria v. 5.0 at 3, 7, 15 and 31 days after the start of study treatment:

- Haematological
    - Neutropenia
    - Thrombopenia
    - Anaemia
    - Lymphopenia
  - Non-haematological
    - CPK increase
    - ALT and/or AST increase
    - Total bilirubin or direct bilirubin increase
    - Neurotoxicity
    - QT-QTc interval prolongation
  - Other ≥ grade 3 adverse events
- The number and percentage of patients in whom treatment cannot be completed and the reasons will be provided.
  - The number and percentage of patients with AEs and SAEs will be provided at 3, 7, 15 and 31 days.
  - The evolution of haematological and non-haematological parameters from the baseline visit on days 3, 7, 15 and 31 will be provided.

*CONFIDENTIAL*

- The number and percentage of patients with ECG abnormalities on days 1, 2, 3, 4, 5, 6, 7, 15 and 31 will be provided. Any alterations detected will be described in detail.

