2.6 Endpoints

Primary endpoints:

To set the safety and toxicological profile of plitidepsin at each dose level administered in patients admitted for COVID-19, the following variables will be analyzed:

- Occurrence frequency of the following grade ≥ 3 adverse events according to the NCI-CTCAE criteria v5.0 at 3, 7, 15 and 31 days:
 - Hematological
 - Neutropenia
 - Thrombocytopenia
 - Anemia
 - Lymphopenia
 - Non hematological
 - CPK increase
 - ALT and/or AST increase
 - Total bilirubin increase or direct bilirubin

- Neurotoxicity
- QT-QTc interval prolongation
- Other grade ≥ 3 adverse events
- Percentage of patients with uncompleted treatment and the reasons.
- Percentage of patients with AEs and SAEs at days 3, 7, 15 and 31.
- Changes from baseline (day -1 or day 1 before administration of study medication) in hematological and non-hematological parameters on days 3, 7, 15, 31.
- Percentage of patients with ECG abnormalities at days 2, 3, 4, 5, 6, 7, 15 and 31.

Secondary endpoints:

- Change from baseline in SARS-CoV-2 viral load (day -1 or day 1 before administration of study medication) measured at 3, 4, 7, 15, and 31 days.
- Time to negative detection of SARS-CoV-2 by PCR obtained in nasopharyngeal swab or sample from the lower respiratory tract compared to baseline (day -2 or -1 or day 1 before administration of study medication).
- Deaths at 7, 15 and 31 days.
- Percentage of patients that need for invasive mechanical ventilation at 7, 15, and 31 days.
- Percentage of patients that need for non-invasive mechanical ventilation at 7, 15, and 31 days.
- Percentage of patients that need for oxygen therapy at 7, 15 y 31 days.
- The recommended dose level will be selected after the evaluation of the safety and efficacy data obtained in this study between the sponsor and the Spanish Agency for Medicines and Health Products.

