APPENDIX II

11 SAFETY EVALUATION

11.1 Safety endpoints

Table 11.1.1 Summary of Protocol-Specified Safety Endpoints. Cumulative results.

Endpoint	Dose Cohort			
	1.5 mg N=X	2.0 mg N=X	2.5 mg N=X	Total N=X
	n (%)			
Patients unable to complete treatment				
Patients with grade ≥ 3 AEs from Day 1 to				
Day 3				
Day 7				
Day 15				
Day 31				
Patients with AEs from Day 1 to				
Day 3				
Day 7				
Day 15				
Day 31				
Patients with SAEs from Day 1 to				
Day 3				
Day 7				
Day 15				
Day 31				
Patients with ≥ 1 grade change in hematological parameters from Day 1 to				
Day 3				
Day 7				
Day 15				
Day 31				
Patients with ≥ 1 grade change in non-hematological parameters, from Day 1 to				
Day 3				
Day 7				
Day 15				
Day 31				
Patients with QTc >60msec from baseline to				
Day 31				

This table will be also performed by age (<65 vs. ≥ 65 year old (11.1.1.1))

Table 11.1.2 Summary of Protocol-Specified Safety Endpoints. Non-cumulative.

Endpoint	Dose Cohort			
	1.5 mg N=X	2.0 mg N=X	2.5 mg N=X	Total N=X
	n (%)			
Patients unable to complete treatment				
Patients with grade ≥ 3 AEs from				
Day 1 to Day 3				
Day 4 to Day 7				
Day 8 to Day 15				
Day 16 to Day 31				
Patients with AEs from				
Day 1 to Day 3				
Day 4 to Day 7				
Day 8 to Day 15				
Day 16 to Day 31				
Patients with SAEs from				
Day 1 to Day 3				
Day 4 to Day 7				
Day 8 to Day 15				
Day 16 to Day 31				
Patients with ≥ 1 grade change in hematological parameters from				
Day 1 to Day 3				
Day 4 to Day 7				
Day 8 to Day 15				
Day 16 to Day 31				
Patients with ≥ 1 grade change in non- hematological parameters, from				
Day 1 to Day 3				
Day 4 to Day 7				
Day 8 to Day 15				
Day 16 to Day 31				

This table will be also performed by age (<65 vs. ≥ 65 year old) (11.1.2.1)

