11.4 Adverse events

Table 11.4.1 Summary of Adverse Events, Regardless of Relationship, by SOC and PT by Dose Cohort and Overall

MedDRA SOC Preferred Term	Dose Cohort			
	1.5 mg N=X	2.0 mg N=X	2.5 mg N=X	Total N=X
	n (%)			
Subjects with any AE				
Gastrointestinal disorders				
Abdominal pain				
Abdominal pain upper				
....				
General disorders and administration site conditions				
Asthenia				
Chest discomfort				
...				

Each patient reported once per Preferred Term; This table will be also performed by age (<65 vs. ≥65 year old) (11.4.1.1)

Listing 11.4.2 All adverse events

Dose cohort	Subject id.	Age	SOC	PT	Serious adverse events	Relationship	Grade	Onset date	End date

Table 11.4.3 Summary of Treatment-Related Adverse Events by SOC and PT by Dose Cohort and Overall

MedDRA SOC Preferred Term	Dose Cohort			
	1.5 mg N=X	2.0 mg N=X	2.5 mg N=X	Total N=X
	n (%)			
Subject with any related AE				
Gastrointestinal disorders				
Abdominal pain				
Abdominal pain upper				
....				
General disorders and administration site conditions				
Asthenia				
Chest discomfort				
...				

Each patient reported once per Preferred Term; This table will be also performed by age (<65 vs. ≥65 year old) (11.4.3.1)

Listing 11.4.4 All Related Adverse Events

Dose cohort	Subject id.	Age	SOC	PT	Serious adverse events	Relationship	Grade	Onset date	End date

Table 11.4.5 Grade ≥3 Adverse Events, Regardless of Relationship by Dose Cohort and Overall

MedDRA SOC Preferred Term	Dose Cohort			
	1.5 mg N=X	2.0 mg N=X	2.5 mg N=X	Total N=X
	n (%)			
Patients with any Grade ≥3 AE				
Blood and lymphatic system disorders				
Leukocytosis				
Gastrointestinal system disorders				
Diarrhea				

Each patient reported once per Preferred Term; This table will be also performed by age (<65 vs. ≥65 year old) (11.4.5.1)

Table 11.4.14 Summary of Adverse Events

Patients	1.5 mg N=X		2.0 mg N=X		2.5 mg N=X		Total N=X	
	N	%	N	%	N	%	N	%
Patients with AEs								
Patients with treatment-related AEs								
Patients with Grade >=3 AEs								
Patients with Grade >=3 treatment-related AEs								
Patients with SAEs								
Patients with treatment-related SAEs								

This table will be also performed by age (<65 vs. >=65 year old) (11.4.14.1)

Listing 11.4.15 Patients Experiencing AEs Leading treatment discontinuation or drug interruption

Dose Cohort	Subject id	Sex	Age	AE treatment discontinuation/Interruption	Relatedness	Study Day of Onset/Death

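### SAP 7.1 puts the named primary safety events at a one-grade change instead of grade 3 or higher, and the available shift-table shells pool the three doses

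*SAP*

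**What the plan says.** Protocol 12.4 sets the analysis of the first primary endpoint: "The number and percentage of patients presenting the following ≥ grade 3 adverse events will be provided", followed by four haematological and five non-haematological events and a line for other events, at days 3, 7, 15 and 31. Protocol 6.2 has the same list. SAP 2.6 repeats it as "Occurrence frequency of the following grade ≥ 3 adverse events according to the NCI-CTCAE criteria v5.0 at 3, 7, 15 and 31 days" and keeps the last line, "Other grade ≥ 3 adverse events". The stated aim in both documents is the safety profile at each dose level.

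SAP 7.1, which says what will be tabulated, gives the same nine events under another measure: "Number and percentage of patients presenting the following adverse events with ≥ 1 grade change in" the listed parameters. It lists AST and ALT separately and has no line for other events. Further down, 7.1 has bullets for patients with any grade 3 or higher event, and two bullets on grade change, the first beginning "Patients with ≥ 1 grade change from baseline in hematologic parameters". All of these carry day windows.

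On presentation, Protocol 12.1 and SAP 7 and 7.2 call for results by treatment arm. The shells for Tables 11.6.1 (haematology shift) and 11.6.2 (chemistry shift) are titled for combined dose groups. The only row block in Table 11.7.5 (QTc shift) is for combined cohorts.

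**The concern.** A programmer working from SAP 7.1 would count patients whose grade moved by at least one step. The protocol asks for patients who reached grade 3 or higher. These are different quantities, and the SAP disagrees with its own section 2.6 about which one belongs to the named list. Protocol 12.5.3 also says the interim safety analyses follow 12.4, so final tables built from the first bullet of 7.1 would not line up with the interim ones on these events.

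The pooling matters because the recommended dose is to be chosen partly from these safety data. A shift table over all doses cannot show whether larger shifts in a laboratory value or QTc cluster at one dose.

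**Working it through.** No power, alpha or sample-size figure is at issue, so there is none to reproduce. The check compares the texts and shells.

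**Step 1. What each place supplies.** The endpoint has 4 + 5 = 9 named events, a line for others, four time points and three doses.

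| Place | Measure | Per named event | By dose | By day |
|---|---|---|---|---|
| Protocol 6.2 and 12.4, SAP 2.6 | grade ≥ 3 | yes, plus others | yes | 3, 7, 15, 31 |
| SAP 7.1, first bullet | ≥ 1 grade change | yes, without others | yes, through SAP 7 | yes, through the lead-in |
| SAP 7.1 later grade-change bullets; rows in Tables 11.1.1 and 11.1.2 | ≥ 1 grade change | no, two lumped groups | yes | yes |
| SAP 7.1 windowed grade ≥ 3 bullet; rows in Tables 11.1.1 and 11.1.2 | grade ≥ 3 | no, any event | yes | yes |
| Table 11.4.5 | grade ≥ 3 | by preferred term | yes | no |
| Table 11.1.1, QTc row | rise over 60 ms | QTc only | yes | to day 31 only |
| SAP 7.3, ECG | ungraded alterations | ECG only | yes | yes |

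No row after the first combines grade ≥ 3, the named event, dose and day. The nearest is "Table 11.4.5 Grade ≥3 Adverse Events, Regardless of Relationship by Dose Cohort and Overall". It covers the whole adverse-event period, which ends 28 days after the last dose. With the last dose on day 3, that is day 3 + 28 = day 31, so the table comes close to the day-31 count for an event that maps to one preferred term. It does not show days 3, 7 and 15. Each patient is counted once per preferred term, so AST and ALT rows cannot be added to give patients with either. The QTc row, "Patients with QTc >60msec from baseline to" Day 31, uses a change in milliseconds and not a grade.

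**Step 2. The two measures differ.** A move from grade 0 to 1, or 1 to 2, counts under 7.1 and not under the protocol. A move from 2 to 3 counts under both. A patient at grade 3 at baseline who stays there shows no grade change; whether that patient counts at grade ≥ 3 depends on whether the finding is recorded as an adverse event. Neither count can be derived from the other.

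**Step 3. Pooling.** The repeats listed under Tables 11.6.1, 11.6.2 and 11.7.5 are by age, by amendment period (one of these only on request) or by inflammatory parameters. None is by dose. Efficacy shells 12.1.33 and 12.1.35 do offer a by-dose version on request; these three do not.

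**Step 4. What pooling can hide (hypothetical).** Patients per dose are 9 + 6 = 15, and 3 × 15 = 45, which agrees with the SAP total. Assume three patients have a given shift, all at one dose. The exact 95% limits are Beta⁻¹(0.025; x, n − x + 1) and Beta⁻¹(0.975; x + 1, n − x).

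- That dose: 3/15 = 20.0% (4.3% to 48.1%).
- Pooled: 3/45 = 6.7% (1.4% to 18.3%).

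With no events, the upper limit is 21.8% for 15 patients and 7.9% for 45.

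**The case against.** The best defence is that the first bullet of 7.1 belongs to another primary endpoint, change from baseline "in haematological and non-haematological parameters on days 3, 7, 15 and 31". Its sub-headings refer to parameters, and the later grade-change bullets lump parameters together, so the first bullet could be the per-parameter version. That reading is possible, and it is a reason to keep the output. It does not close the gap, because the named events at grade ≥ 3 then have no entry of their own in 7.1.

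A second defence combines scattered text. The 7.1 lead-in says results are presented on days 3, 7, 15 and 31. Events are grouped by system organ class and preferred term, and further bullets promise grade ≥ 3 events and events by grade and dose. Together these might be meant to cover grade ≥ 3 by term, dose and day. But those further bullets carry no day windows, and no available shell shows the combination.

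Third, shells 11.4.6 to 11.4.13 and 11.7.2 to 11.7.4 do not appear in the text reviewed and may hold part of what is missing. This stands, and it limits any statement about outputs. It does not change the wording of 7.1 or the layout of the three pooled shells.

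It also stands that separate AST and ALT rows are finer reporting, that the protocol does not itself ask for shift tables, and that SAP 7.2 plans percentage change by arm.

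**Conclusion.** The point holds and should be fixed. SAP 7.1 does not carry through the grade ≥ 3 definition of the named events that the protocol and SAP 2.6 give. On either reading of its first bullet, grade ≥ 3 per named event by dose and day is absent from 7.1 and from the available shells. In those shells, the size of grade shift per parameter is also not shown by dose.

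Three stronger readings are not supported.

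- A reader might infer that grade ≥ 3 reporting has been dropped or the endpoint redefined. SAP 2.6 keeps the definition, Tables 11.1.1 and 11.1.2 give any grade ≥ 3 event by dose and day, and Table 11.4.5 gives it by term and dose.
- A reader might infer that safety, or grade change, is tabulated only over pooled doses. Many safety tables are by dose, SAP 7.1 with SAP 7 implies a per-parameter ≥ 1 grade change count by arm, and some shells were not available.
- A reader might use the phase I tables in Protocol Annex 7 to size the difference between the two measures. Those tables give worst grades and not grade changes, so they do not measure it.

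No data are lost: Listing 11.4.2 carries dose, term, grade and onset date. The analysis is descriptive, so no test or error rate is affected. The numerical effect on the counts cannot be estimated from the documents; the pooling figures in the check rest on an assumed three events at one dose. Confidence is high on the wording conflict and medium on what the outputs lack, because of the absent shells.

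**What to change.** 1. In SAP 7.1, state the named events at grade ≥ 3, cumulative to days 3, 7, 15 and 31, by dose and total. Include the composite of ALT and/or AST (separate AST and ALT rows may stay) and the line for other grade ≥ 3 events. If an existing shell already does this, refer to it in 7.1.
2. Keep the ≥ 1 grade change count as a separate summary, still per parameter and by arm, and label it as support for the change-from-baseline endpoint.
3. Produce Tables 11.6.1, 11.6.2 and 11.7.5 by dose as well as combined.

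The cost is SAP wording, some table rows and by-dose versions of three shells. No new data are needed, and the endpoint and its data source do not change.
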